10.2.9 Discontinuation of the Study, and Discontinuation of Study Site Participation

The Sponsor or its delegate may stop the study or study site participation in the study for medical, safety, regulatory, administrative, or other reasons according to applicable regulations, rules and GCP. In the event the Sponsor prematurely terminates a particular study site, the Sponsor will promptly notify the study site's IRB/IEC of that.

Post-marketing Clinical Study Protocol Number-Version Number: 851-00

10.3 Appendix 3: Clinical Laboratory Tests

The laboratory tests shown in Table 4 will be performed at the study site at each assessment point. However, blood sampling for laboratory tests (screening test, 24 hours before and after study drug administration) will be performed after confirming the elapse of at least 8 hours after a meal.

Table 4 Protocol-specified Safety Laboratory Tests

| Laboratory Test Category | Parameters | | | | |
|-----------------------------|--|-----------|--|--|---|
| Hematology | Platelet count | | WBC count and differential: Neutrophils, | | |
| | RBC count | | lyı | lymphocytes, monocytes, eosinophils, basophils | |
| | Hemoglobin | | | | |
| | Hematocrit | | | | |
| Clinical Chemistry | Blood urea nitrogen | Potassiun | 1 | AST | Total bilirubin (and direct bilirubin, if total bilirubin is elevated above the upper limit of normal) |
| | Albumin | Chloride | | Fasting blood glucose | Creatinine |
| | Sodium | ALT | | Total protein | Creatine kinase |
| Urinalysis | Specific gravity Urinalysis for pH, glucose, protein and occult blood Microscopy (if urine occult blood or protein is abnormal) | | | | |
| Other Tests | Serology: hepatitis B surface antigen, hepatitis C virus antibody, syphilis and HIV antigen and antibody (CRF completion not required) Drug screen: benzodiazepines, barbiturates, tricyclic antidepressants, phencyclidines, stimulants, cannabis, cocaine, morphine (CRF completion not required) | | | | |

The investigator must review each clinical laboratory result and document the results of review.

Post-marketing Clinical Study Protocol Number-Version Number: 851-00

10.4 Appendix 4: AE Definition and Procedures for Recording, Evaluating, Follow-up, and Reporting

10.4.1 Definition of AE

AE Definition

- An AE is any untoward medical occurrence in a patient or clinical study participant, temporally associated with the use of a study drug, whether or not considered related to the study drug.
- Note: In other words, an AE denotes any unfavorable or unintended sign (including an abnormal laboratory finding), symptom, or disease (new or exacerbated) temporally associated with the use of a study drug.
- Note: For purposes of AE definition, the use of a study drug (also referred to as Sponsor's product in this Appendix) includes the use of any pharmaceutical product, biological product, vaccine, medical device, diagnostic agent, or protocol-specified procedure whether investigational (including placebo or active comparator product) or marketed, manufactured by, licensed by, provided by, or distributed by the Sponsor for human use in this study.

Events meeting the AE definition

- Any abnormal laboratory test (hematology, clinical chemistry, or urinalysis)
 results or other abnormal safety assessments (e.g., ECG, imaging assessments,
 vital sign measurements), including those that worsen from baseline, or those
 considered clinically significant in the medical and scientific judgment of the
 investigator.
- Exacerbation of a chronic or intermittent pre-existing condition including an increase in frequency and/or intensity of the condition.
- A new condition detected or diagnosed after the initiation of study drug administration whether or not it may have been present before the start of the study.
- Signs, symptoms, or sequelae of a suspected drug-drug interaction.
- Signs, symptoms, or sequelae of a suspected overdose of either study drug or a concomitant medication.
- For any reports of overdose (whether accidental or intentional) with an
 associated AE, the AE term should reflect the relevant clinical symptom or
 abnormal test result. An overdose without any associated clinical symptoms or
 abnormal laboratory results is reported using the terminology "accidental or
 intentional overdose without adverse effect" or "intentional overdose without
 adverse effect."
- Any new cancer or progression of pre-existing cancer.

Events **NOT** meeting the AE definition

- Medical or surgical procedure (e.g., endoscopy, appendectomy): a condition that leads to the procedure is the AE.
- Situations in which an untoward medical occurrence did not occur (social and/or convenience admission to a hospital).

Post-marketing Clinical Study Protocol Number-Version Number: 851-00

- Anticipated day-to-day fluctuations of pre-existing disease(s) or condition(s) present or detected at the start of the study, or such a present or detected disease(s) or condition(s) that does not worsen.
- Surgery planned prior to informed consent to treat a pre-existing condition that has not worsened.
- Refer to Section 8.4.6 for protocol-specific exceptions.

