8.3.4 Safety Laboratory Tests

- Refer to Appendix 3 for the list of clinical laboratory tests to be performed for this study, and to "1.3 Study Schedule" for the timing and frequency of tests.
- The investigator will review laboratory reports, document this review, and record any clinically meaningful changes occurring during the study in the adverse event form in the case report form (CRF). Laboratory reports will be filed with the source documents. Clinically significant abnormal laboratory findings are abnormal findings which are not associated with the participant's underlying disease, unless judged by the investigator to be more severe than expected for the participant's condition.

Post-marketing Clinical Study Protocol Number-Version Number: 851-00

• If laboratory results from non-protocol-specified laboratory assessments performed at the study site require a change in study participant management or are considered clinically significant by the investigator (e.g., serious adverse event, adverse event, or dose modification of the study drug), the results will be recorded in the appropriate CRF (e.g., SLAB).

• For any clinically significant abnormal laboratory findings during the study or within 14 days after study drug administration, every attempt will be made to perform repeat assessments until the values return to normal or baseline, or until a new baseline is established as determined by the investigator.

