8.4 Adverse Events (AEs), Serious Adverse Events (SAEs), and Other Reportable Safety Events

The definitions of an AE or SAE, as well as the method of recording, evaluating, and assessing causality of AE and SAE and the procedures for preparing and transmitting AE, SAE, and other reportable safety event reports are shown in Appendix 4.

AEs, SAEs, and other reportable safety events will be reported by the participant (or, when appropriate, by a caregiver, surrogate, or the participant's legally authorized representative).

The investigator will detect, document, and report events that meet the definition of an AE or SAE as well as other reportable safety events. The investigator will also continue to follow up AEs, SAEs, and other reportable safety events for outcome according to Section 8.4.3.

The investigator will assess events that meet the definition of an AE or SAE as well as other reportable safety events with respect to seriousness, intensity/Grade and causality with the study drug.

8.4.1 Time Period and Frequency of Reporting AEs, SAEs, and Other Reportable Safety Events

All AEs, SAEs, and other reportable safety events that fall under any of the following criteria occurring after the consent form is signed but before treatment allocation will be reported by the investigator for only participants assigned to treatment: the event led to study withdrawal; and the event is the result of a protocol-specified medical intervention (e.g., washout or discontinuation of usual therapy, diet, or a procedure).

From the time of treatment allocation through 14 days after study drug administration, all AEs, SAEs and other reportable safety events occurring will be reported by the investigator.

Additionally, any SAE brought to the attention of the investigator any time outside of the time period specified in the previous paragraph will also be reported immediately to the Sponsor if the event is considered "related" to the study drug.

Post-marketing Clinical Study Protocol Number-Version Number: 851-00

The investigator is not obligated to actively seek AE or SAE or other reportable safety events in former study participants. However, if the investigator learns of any SAE, including a death, at any time after a participant has been discharged from the study, and he/she considers the causality between the event and the study drug (or study participation) to be a reasonable possibility (related), the investigator must promptly report to the Sponsor.

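### Does the adverse event definition turn every out-of-range laboratory value into an adverse event, and does that need fixing?

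*Combined protocol and SAP*

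**What the plan says.** Section 8.4 points to Appendix 4 for "The definitions of an AE or SAE, as well as the method of recording, evaluating, and assessing causality of AE and SAE". Section 8.4.1 then requires that, from allocation to 14 days after dosing, "all AEs, SAEs and other reportable safety events occurring will be reported by the investigator".

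Appendix 4, section 10.4.1, defines an AE as something untoward occurring in temporal association with the study drug. A note restates this as "any unfavorable or unintended sign (including an abnormal laboratory finding), symptom, or disease (new or exacerbated"). The list of qualifying events opens with "Any abnormal laboratory test (hematology, clinical chemistry, or urinalysis") results. It adds other abnormal safety assessments, and names worsening from baseline and clinical significance in the investigator's judgment as included cases. The list of non-qualifying events covers a pre-existing state, or "such a present or detected disease(s) or condition(s) that does not worsen".

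Section 8.3.4 tells the investigator to review laboratory reports and "record any clinically meaningful changes occurring during the study in the adverse event form in the case report form (CRF"). It continues: "Clinically significant abnormal laboratory findings are abnormal findings which are not associated with the participant's underlying disease", with an exception where the investigator judges the finding worse than expected for that participant.

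Section 10.4.4 grades intensity. Mild means minimal discomfort with no interference in daily activity. Moderate means discomfort described as severe, with interference. Severe means that daily activity is prevented.

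**The concern.** The two sections set different thresholds for the same form. In 10.4.1, worsening and clinical significance are introduced as examples, so on the page they do not limit the word that opens the bullet. A slightly high creatine kinase at 24 hours would then be an AE under Appendix 4, while 8.3.4 gives no instruction to record it. The 8.3.4 account of clinical significance leans on underlying disease, which looks like a poor filter in healthy volunteers.

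The endpoint table in section 3 counts laboratory values within AEs, and section 9.2.2 makes all AEs primary. With 12 participants and no control group, chance abnormalities entered as AEs could make a single dose look less well tolerated than it is, with no background rate for comparison.

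The moderate grade also appears to skip a level: discomfort goes from minimal under mild to severe under moderate, which might leave intermediate events without a grade.

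**Working it through.** The plan gives no figure on this point, so the check is mainly of the text.

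**Do the two sections conflict?** Section 8.3.4 does not say that only clinically meaningful changes go on the form. It is an instruction for reviewing laboratory reports; Appendix 4 holds the definition. A site that records more than 8.3.4 asks for breaches neither. They are two thresholds left unreconciled, not a contradiction.

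**Is the literal reading the only one?** The bullet sits under a definition whose test is that the occurrence be untoward, restated as unfavorable or unintended. If every abnormal value qualified automatically, the closing reference to investigator judgment of clinical significance would do no work. The wording is loose, and the narrower reading is at least as natural.

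**Does the 8.3.4 description of clinical significance separate anything here?** Yes, to a degree. Appendix 6 admits participants whose abnormal value comes from a permitted co-existing condition, with eosinophilia from asthma or seasonal allergy as its example. The 8.3.4 sentence also already contains investigator judgment, through its exception.

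**How many participants could the literal reading affect?** "The laboratory tests shown in Table 4 will be performed at the study site at each assessment point", and the only scheduled post-dose laboratory draw is at 24 hours (section 1.3). Table 4 lists 22 blood analytes: 10 hematology (platelets, red cells, hemoglobin, hematocrit, white cells and 5 differential counts) and 12 chemistry. Assume each is newly abnormal with probability p, independently. The chance of at least one per participant is 1 − (1 − p)^22, and the expected number of participants is 12 times that. To allow for correlation, the last column repeats the calculation with an assumed 11 effective analytes.

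| Assumed p | 1 − (1 − p)^22 | Expected of 12, 22 analytes | Expected of 12, 11 effective |
|---|---|---|---|
| 0.5% | 0.104 | 1.25 | 0.64 |
| 1% | 0.198 | 2.38 | 1.26 |
| 2% | 0.359 | 4.31 | 2.39 |
| 5% | 0.676 | 8.12 | 5.17 |

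The rates, the independence and the figure of 11 are all assumptions. Participants are also assessed on screening and predose laboratory values (sections 5.1 and 10.6), and repeat values within a person are correlated, so the upper rates for newly abnormal results have no support in the documents.

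**What uses the AE count?** Section 9.2.5 states that no hypotheses are tested, and section 4.4.1 that there are no prespecified early termination criteria. Section 9.2.4 describes summaries of laboratory values, ECGs and vital signs with changes from baseline; it specifies no statistic built on the number of AEs. Section 9.2.2 lists laboratory results as a primary endpoint in their own right, so the same values are reported however the site fills in the AE form.

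**Does the intensity scale have a gap?** On function it is complete: not interfering, interfering, preventing. An event that interferes without preventing fits only the moderate grade, whatever adjective is attached to the discomfort.

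**The case for a change.** The strongest argument for a change is that the definition governs a primary endpoint, and a primary endpoint should not depend on how a site reads one bullet. The carve-out for unchanged pre-existing states speaks of diseases and conditions, so it does not plainly cover an abnormal baseline value that Appendix 6 allows as not clinically significant. Section 9.2.4 gives no counting rule to settle the matter. Each AE also brings intensity and causality assessments and follow-up, so the literal reading has a real cost to the site. Clearer wording would need no new data.

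The drafting criticism stands: the sections were not written to match, and the moderate grade reads awkwardly. The inference that the results are at risk does not stand. Limiting laboratory AEs to clinically significant findings is one convention; capturing them broadly in a study whose primary aim is safety is another, and reasonable statisticians differ. The study has a single site, so differing practice between sites cannot arise. With 12 participants, each laboratory AE can be read alongside its intensity, its causality assessment and the laboratory value itself.

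**Conclusion.** No change to the plan follows. The laboratory AE wording is a gap that the investigator and analysts can fill sensibly by applying one convention throughout and describing it in the report. The moderate grade is a clerical slip that alters neither AE counts nor the functional ordering of the grades.

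The effect is confined to the number of laboratory AEs entered. Clinical-symptom AEs, the laboratory summaries and the pharmacokinetic results are the same under either reading. How many entries would differ cannot be fixed from the documents: the illustrative 0.6 to 8.1 of 12 participants rests entirely on assumed rates. The conclusion rests on two features of the plan: no decision or planned statistic depends on the AE count, and laboratory results are reported in full in their own right.

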10.4.2 Definition of SAE

If an event is not an AE per definition above, then it cannot be an SAE even if serious conditions defined below are met.

An SAE is defined as any untoward medical occurrence that, at any dose:

- a. Results in death
- b. Is life-threatening
 - A "life-threatening" occurrence in the definition of "serious" refers to an event in
 which a participant was at risk of death at the time of its onset. It does not refer
 to an event, which hypothetically might have caused death, if it were more
 severe.
- c. Requires inpatient hospitalization or prolongation of existing hospitalization
 - Hospitalization is defined as an inpatient admission, regardless of the length of stay, including admission as a precautionary measure for observation. (Note: Hospitalization for an elective procedure to treat a pre-existing illness that has not worsened during the study is not an SAE. A clinical condition that is detected prior to the use of an MSD product is documented in the participant's medical history.)
- d. Results in permanent or significant disability/incapacity
 - The term "disability" means a substantial disruption of a person's ability to conduct normal life functions.
 - This definition is not intended to include events of relatively minor medical significance such as uncomplicated headache, nausea, vomiting, diarrhea, influenza, and accidental trauma (e.g., sprained ankle) that may interfere with everyday life functions but do not constitute a substantial disruption.
- e. Is a congenital anomaly/birth defect
 - In the offspring of a participant taking the study drug regardless of the time of diagnosis.
- f. Other medically important events
 - Medical or scientific judgment will be exercised in deciding whether SAE reporting is appropriate in the situations described below. Important medical events that, even if they are not immediately life-threatening or they do not result in hospitalization or death, may jeopardize the participant or may require medical or surgical intervention to prevent serious conditions listed in the above definition are usually considered serious.
 - Examples of such events include invasive or malignant cancers, intensive treatment in an emergency room or at home for allergic bronchospasm, blood

Post-marketing Clinical Study Protocol Number-Version Number: 851-00

dyscrasias or convulsions that do not result in hospitalization, or development of drug dependency or drug abuse.

10.4.3 Additional Events to be Reported in the Same Manner as SAE

Additional events that should be reported in the same manner as SAE

- Events listed below, although not included in SAEs specified in ICH, are reportable to the Sponsor in the same timeframe as SAEs to meet certain local requirements. Therefore, these events are regarded as serious.
- A new cancer (that is not a condition of the study)
- An AE associated with an overdose

10.4.4 Recording AE and SAE

AE and SAE recording

- When an AE/SAE occurs, it is the responsibility of the investigator to review all
 documentation (e.g., hospital clinical records, laboratory reports, diagnostic
 reports) related to the event.
- The investigator will enter all relevant AE/SAE information on the AE form on the CRF and worksheets.
- It is not acceptable for the investigator to send photocopies of the participant's medical records to the Sponsor in lieu of recording on the AE form of the CRF.
- There may be instances when copies of medical records for certain cases are requested by the Sponsor. In this case, all participant identifiers (with the exception of the participant number assigned for this study), will be blinded on the copies of the medical records before submission to the Sponsor.
- The investigator will attempt to establish a diagnosis of the event based on signs, symptoms, and/or other clinical information. In such cases, the diagnosis (not the individual signs/symptoms) will be documented as the AE/SAE.

Assessment of intensity

- "Severe" intensity of an AE is not a definition of an SAE. An event is classed as "serious" when it meets at least 1 of the conditions prespecified in the definition of an SAE.
- The investigator will make an assessment of intensity for each AE and SAE (and other reportable safety event) reported during the study and assign it to 1 of the following categories:
- Mild: An event that is easily tolerated by the participant, causing minimal discomfort, but not interfering with everyday activities (for pediatric studies, awareness of symptoms, but easily tolerated).
- Moderate: An event causing severe discomfort that interferes with normal everyday activities (for pediatric studies, definitely acting like something is wrong).
- Severe: An event that prevents normal everyday activities. An AE that is
 assessed as severe should not be confused with an SAE. Severe is a category

Post-marketing Clinical Study Protocol Number-Version Number: 851-00

used for rating the intensity of an event; and both AE and SAE can be assessed as severe (for pediatric studies, extremely distressed or unable to do usual activities).

Assessment of causality

- Did the Sponsor's product cause the AE?
- The determination of the likelihood that the Sponsor's product caused the AE will be provided by the investigator. A signature (autograph, seal, and initials are also acceptable)/date will be provided by the investigator on the source document or worksheet that supports the causality noted on the AE form, ensuring that a medically qualified assessment of causality was done. The document with a signature (autograph, seal, and initials are also acceptable) must be retained for the time frame specified in regulatory requirements. The assessment criteria below are intended as reference guidelines to assist the investigator in assessing the likelihood of a relationship between an AE and the Sponsor's product based upon the available information.
- The following conditions are to be used for causality assessment; the greater the correlation with these conditions and their respective criteria (the number of applicable items or intensity), the more likely the Sponsor's product caused the AE:
- Exposure to the Sponsor's product: The presence or absence of evidence that the participant was actually exposed to the Sponsor's product such as; a reliable dosing record, a reliable record of compliance assessment (pill count, participant diary, etc.), a record of the presence or absence of expected drug effect, or a record related to the measurement of drug/metabolite in the body
- Temporal relationship: Did the AE follow in a reasonable temporal sequence from administration of the Sponsor's product? Is the time of onset of the AE compatible with an effect induced by the Sponsor's product?
- Likely cause: Is it unable to explain the AE reasonably by other cause than the Sponsor's product (underlying disease, other drug(s)/vaccine(s), medical history or other participant or environmental factors)?
- Dechallenge: Was the Sponsor's product discontinued or its dose reduced?
- Did the AE resolve or improve by discontinuation or dose reduction?
- If "yes," this is a positive dechallenge.
- If "no," this is a negative dechallenge.

Note: The dechallenge criterion is not applicable if:

- (1) the outcome of the AE resulted in death or permanent disability
- (2) the AE resolved/improved despite continuation of the study product
- (3) the study is a single-dose study
- (4) Sponsor's product(s) is/are used only 1 time
- Rechallenge: Was the participant re-exposed to the Sponsor's product?
- Did the AE recur or worsen by re-exposure?
- If "yes," this is a positive rechallenge.
- If "no," this is a negative rechallenge.

Note: The rechallenge criterion is not applicable if:

Post-marketing Clinical Study Protocol Number-Version Number: 851-00

- (1) the outcome of the AE resulted in death or permanent disability
- (2) the study is a single-dose study
- (3) Sponsor's product(s) is/are used only 1 time

Note: If a rechallenge is planned for an AE that was serious and suspected to be relate to the Sponsor's product, or if re-exposure to the Sponsor's product poses additional potential significant risk to the participant, then the rechallenge must be approved in advance by the Sponsor development director/medical expertise, and if required, the IRB/IEC.

- Consistency with study drug profile: Is the onset of the AE consistent with previous knowledge regarding the Sponsor's product or drug class pharmacology or toxicology?
- The assessment of relationship will be documented on the CRFs/worksheets by an investigator according to his/her best clinical judgment, including consideration of the above elements.
- Use the following criteria as guidance (not all criteria need to be met to be indicative of a relationship with the Sponsor's product).
- Related: There is a reasonable possibility of a relationship with the Sponsor's product.
 - There is evidence of exposure to the Sponsor's product. The temporal sequence of the AE onset relative to the administration of the Sponsor's product is reasonable. The cause of the AE is more likely explained by the Sponsor's product than by other factors (other drugs, underlying disease, medical history, or other participant or environmental factors).
- Not related: There is not a reasonable possibility of a relationship with the Sponsor's product.
 - The participant did not receive the Sponsor's product, the temporal sequence of the AE onset relative to the administration of the Sponsor's product is not reasonable, or the cause of the AE is more likely explained by another cause than the Sponsor's product. (An overdose without an associated AE is also considered as "not related.")
- For each AE/SAE, the investigator must document in the medical records that he/she has reviewed the AE/SAE and has provided an assessment of causality.
- There may be situations in which an SAE has occurred and the investigator has
 minimal information to include in the initial report to the Sponsor. However,
 even in such cases, it is very important that the investigator always make an
 assessment of causality for every event before the initial transmission of the SAE
 data to the Sponsor.
- The investigator may change his/her opinion on causality in light of follow-up information and send an SAE follow-up report with the updated causality assessment.
- The causality assessment is 1 of the criteria used when determining regulatory reporting requirements.

Post-marketing Clinical Study Protocol Number-Version Number: 851-00

Follow-up of AE and SAE

The investigator is obligated to arrange for the conduct of supplemental
measurements and/or evaluations or perform them as medically indicated or as
requested by Sponsor to elucidate the nature and/or causality of the AE or SAE
as fully as possible. This may include additional laboratory tests or assessments,
histopathological examinations, or consultation with other health care
professionals.

- New or updated information will be recorded in the CRF.
- The investigator will submit any additional information on SAE to the Sponsor within 24 hours of receipt of the information.

